9.3.2 Analysis of Secondary Efficacy Variable

9.3.2.1 Definition of Variables

The secondary endpoint is the absolute change from baseline in total step count per day to the average of Week 8 through Week 12.

Total step count per day will be measured by the wrist-worn actigraphy sensor on each calendar day. The wrist-worn device will be worn 24 hours per day continuously from Day -14 throughout the Treatment Period. The daily assessment is considered as valid if there are at least 10 cumulative hours of valid wear (excluding periods of non-wear, no data, and artifact [noise]) while awake on that day.⁴ The 2-week baseline period and 12-week treatment period will be divided into 14 weekly intervals (Day -14, Day -7, Week 1, Week 2, ..., Week 12), and the average of total step count per valid day will be calculated for each weekly interval, provided that there are valid daily assessments on at least 3 weekdays and 1 weekend day.

The baseline value will be defined as the average of valid weekly interval measurements prior to the first dose of study drug (e.g., average of Day -14 and Day -7). If one weekly interval measurement is missing or invalid, the non-missing, valid interval measurement will be used.

9.3.2.2 Analysis Method

The analysis will be based on an MMRM model similar to the analysis of the primary efficacy variable (without any natural log transformation), with change from baseline at each post-baseline weekly interval (Week 1 to Week 12) as the dependent variable. The model will include the weekly intervals as fixed effects and baseline total step count per day as a covariate.

The primary result obtained from the model will be the estimated mean change from baseline to the average of Week 8 through Week 12. The estimated mean change and 2-sided 95% confidence interval will be provided. Furthermore, the estimated mean change at each post-baseline weekly interval will also be provided. The estimated mean change at each post-baseline weekly interval up to Week 12 will be plotted.

[figure not shown]
In addition, the post-baseline raw values and the change from baseline at each post-baseline weekly interval up to Week 12 will be summarized descriptively (n, mean, SD, median, minimum, and maximum).

[figure not shown]
9.3.2.3 Multiplicity Adjustment

Not applicable.

9.3.2.4 Sensitivity Analysis

Not applicable.

9.4 Safety Analysis

All safety analyses will be based on data from the TE period in the Safety Set, unless otherwise specified.

The overall safety profile of study drug will be assessed in terms of the following safety and tolerability endpoints:

- Treatment-emergent adverse events (TEAEs)
- Clinical laboratory values

Only descriptive analysis of safety will be performed. No statistical testing will be performed. Note that post-baseline safety measurements (except TEAEs) are only scheduled at Week 13.

9.4.1 Adverse Events

For analysis purposes, AEs will be classified as pretreatment AEs, TEAEs during the Treatment Period, and post-treatment AEs, defined as follows:

- **Pretreatment AE:** any AE that occurred before the first dose date of study drug.
- **TEAE during the Treatment Period:** any AE that worsened (either in severity or seriousness) or that was newly developed at or after the first dose date of study drug through the end of the TE period
- **Post-treatment AE:** any AE that worsened (either in severity or seriousness) or that was newly developed after the TE period.

For AEs with completely missing or partially missing start dates, if there is no clear evidence that the AEs were pretreatment or post-treatment, the AEs will be classified as TEAEs.

Details for imputing missing or partial start dates of adverse events are described in Appendix D.

An overview of all TEAEs will be provided with the following categories:

- Number of TEAEs
- Subjects with any TEAEs
- Subjects with TEAEs by strongest relationship
- Subjects with TEAEs by maximum severity
- Subjects with TEAEs leading to study drug discontinuation
- Subjects with TEAEs leading to study drug interruption
- Subjects with Grade 3/4/5 TEAEs
- Subjects with related TEAEs

- Subjects with serious TEAEs
- Subjects with related serious TEAEs
- Subjects with TEAEs leading to death

The following summary tables of TEAEs will be presented by MedDRA System Organ Class (SOC) and Preferred Term (PT) using frequency counts and percentages (i.e., number and percentage of subjects with an event):

- All TEAEs
- Grade 3/4/5 TEAEs
- TEAEs by strongest relationship
- TEAEs by maximum severity
- TEAEs leading to treatment discontinuation
- TEAEs leading to treatment interruption
- Related TEAEs
- Serious TEAEs
- Related serious TEAEs
- TEAEs leading to death

Summaries will be presented by MedDRA SOC and PT using frequency counts and percentages (i.e., number and percentage of subjects with an event). When summarizing the number and percentage of subjects, subjects with multiple occurrences of the same AE or a continuing AE will be counted once and only the maximum severity level will be presented in the severity summaries, and the strongest relationship level will be presented in the relationship summaries.

All AEs, including pretreatment AEs, TEAEs, and post-treatment AEs, will be presented in an individual subject data listing based on the All Subjects Set. In addition, a listing containing individual subject adverse event data for TEAEs leading to treatment discontinuation, TEAEs leading to treatment interruption, Grade 3/4/5 TEAEs, SAEs and all deaths will be provided. Listings for SAEs and deaths will include a flag indicating the TEAE status.

9.4.1.1 Adverse Events of Special Interest

For this study, elevated transaminase events and rash events, as determined by MedDRA preferred terms in Appendix E, are considered as adverse events of special interest.

For treatment-emergent elevated transaminase events and rash events, the following categories will be summarized by treatment group:

- Subjects with events
- Subjects with events by maximum severity
- Subjects with events leading to treatment discontinuation
- Subjects with events leading to treatment interruption

- Subjects with serious events
- Subjects with related serious events
- Subjects with events leading to death
- Duration of events
- Time-to-onset of first event

In addition, for treatment-emergent rash events, these categories will be summarized for the following subgroups:

- Sex (male, female)
- Female subjects with concomitant hormonal therapy (Yes, No)

9.4.2 Clinical Laboratory

[figure not shown]
For the treatment-emergent laboratory measurements, the observed values and change from baseline values of the continuous serum chemistry results will be summarized in SI units at each clinic visit.

[figure not shown]
The number and percentage of subjects meeting at least 1 threshold analysis criterion, during the TE period will be summarized. The threshold analysis of shift from baseline will also be summarized for liver function tests (LFTs) laboratory parameters. The threshold analysis criteria are provided in Appendix F.

For selected LFTs, (alanine transaminase [ALT], aspartate transaminase [AST], alkaline phosphatase [ALP], and total bilirubin), a scatter plot of the maximum treatment-emergent value versus the baseline value corresponding to \times ULN (upper limit of normal) will be presented. Further, a scatter plot of the maximum treatment-emergent value of ALT and AST, separately, versus the maximum treatment-emergent value of total bilirubin corresponding to \times ULN will also be presented.

Results of urinalysis and positive urine/serum pregnancy test will be listed in individual subject data listings only. For positive serum pregnancy listing, subjects with serum HCG which are above non-pregnant levels will be selected.

[figure not shown]
In addition, a listing containing individual subject chemistry values will be provided. This listing will include data from both scheduled and unscheduled visits.

9.4.6 Physical Examination

Abnormal PE findings will be presented as an individual subject data listing only.

9.4.8 COVID-19 Impacted Visits

A listing containing subjects' visits impacted due to COVID-19 will be provided.

10 Interim and DMC Analyses

10.1 Interim Analysis

Not applicable.

10.2 DMC analysis

Not applicable.

12 LIST OF APPENDICES

Appendix A: Analysis Visit Windows for Safety and Efficacy Assessments

Table 12-1 Analysis Visit Windows for Safety and Efficacy Assessments			
Assessment	Visit¹	Target Study Day²	Analysis Visit Window (in study days)^{3, 4, 5, 6}
Safety Assessment			
Serum Chemistry	Day 1 (Baseline)	1	≤1 Pre-dose
	Week 13	85	[57, 99]
	Safety Follow-up	Not applicable	Use nominal visit
[REDACTED]			
BMI, Weight, Height and their Z-scores	Day 1 (Baseline)	1	≤1 Pre-dose
	Week 13	85	[57, 99]
	Safety Follow-up	Not applicable	Use nominal visit
Efficacy Assessment			
Cough frequency ⁷	Day -14	-14	[-28, -8] Pre-dose
	Day -7	-7	[-7, 1] Pre-dose
	Week 2	8	[1, 14] Post-dose
	Week 3	15	[15, 21]
	Week 4	22	[22, 28]
	Week 5	29	[29, 35]
	Week 6	36	[36, 42]
	Week 7	43	[43, 49]
	Week 8	50	[50, 56]
	Week 9	57	[57, 63]
	Week 10	64	[64, 70]
	Week 11	71	[71, 77]
Week 12	78	[78, 92]	
Step count [REDACTED]	Day -14	Not applicable ²	≤-8 (7-day window)
	Day -7		[-7, -1]
	Week 1		[1, 7]
	Week 2		[8, 14]
	Week 3		[15, 21]
	Week 4		[22, 28]
	Week 5		[29, 35]
	Week 6		[36, 42]
	Week 7		[43, 49]
	Week 8		[50, 56]
	Week 9		[57, 63]
	Week 10		[64, 70]
Week 11		[71, 77]	
Week 12		[78, 84]	

Table 12-1 Analysis Visit Windows for Safety and Efficacy Assessments

Notes:

¹ Visit name for analysis purpose is used to report data in tables and figures. In this context, visit may not necessarily refer to a clinic visit and can include telemedicine contact or wearable device measurement.

² Step count and [REDACTED] are measured on a weekly basis, so this column denotes the first day of the 7-day interval.

³ The analysis visit windows will be applied using the following rules for both scheduled and unscheduled visits:

- a. If no numerical measurement is available within a visit window, the measurement will be considered missing for the visit.
- b. If there is more than 1 numerical measurement available within a visit window, use the following rules:
 - i. The measurement closest to the target day will be used; or
 - ii. If there are multiple measurements with the same distance from the target day, the latest measurement will be used.

⁴ For lab, ECG and vital sign measurement collected on the date of first dose of study drug, if it cannot be determined whether the measurement is before or after the first dose:

- a. Scheduled measurement will be treated as pre-dose observation.
- b. Unscheduled measurement will be treated as post-dose observation.

⁵ For safety assessments, the Safety Follow-up analysis visit will be based on the nominal Safety Follow-up visit. If a subject doesn't have a nominal Safety Follow-up visit but has an ETT visit with study day > nominal Week 13 visit, then the ETT visit will be mapped into Safety Follow-up analysis visit.

⁶ For nutrition variables (BMI, Weight, Height and their Z-scores), if there are multiple assessments > nominal Week 13 visit, then the nominal Safety Follow-up visit will be mapped to the Safety Follow-up visit. If there is only ETT assessment > nominal Week 13 visit, the ETT visit will be mapped to the Safety Follow-up visit; else if there are multiple assessments with > nominal Week 13 visit then select the earliest record.

Derived Variables:

1. Age (in years) at first dose date and nominal visit (for demographics, listing and the calculation of [percent] predicted spirometry variables):

Obtain the age at informed consent (in days) in "yy, mm" format (e.g., 24 years, 6 months) from the Vital Signs (VS) page at the Screening Visit, and add 0.5 month to convert to days.

Obtain the informed consent date.

Then age (in years) at first dose or nominal visit = [(first dose date or nominal visit date – informed consent date) in days + age at informed consent (in days)]/365.25.

2. Age (in months) at nominal visit (for use in calculation of BMI and weight z-score):

Obtain the age at informed consent (in months) in "yy, mm" format (e.g., 24 years, 6 months) from Vital Signs (VS) page at the Screening Visit.

Obtain the informed consent date.

Table 12-1 Analysis Visit Windows for Safety and Efficacy Assessments

Assessment	Visit ¹	Target Study Day ²	Analysis Visit Window (in study days) ^{3, 4, 5, 6}

Then age (in months) at nominal visit = integer part of $\{[(\text{age at informed consent (in months)} + 0.5 + \text{diff}(\text{first dose date or nominal visit date, informed consent date}) \text{ in months})] + 0.5$.
			

3. Missing first dose date or last dose date
 
If the first dose date is missing, use Day 1 visit date to impute.
 
If the last dose date is missing or partial date is reported, the last dose date will be imputed based on, in descending order priority, the Early Treatment Termination (ETT) visit date, last visit date before the Safety Follow-up, or the last study drug administration date from EX SDTM domain, as appropriate. The imputation algorithm will ensure the imputed last dose date does not exceed the study participation end date.
			

⁷ The baseline value is defined as the geometric mean of valid cough measurements prior to the first dose of study drug (e.g., Day -14 and Day -7). If one value is missing or invalid, the non-missing, valid value will be used. If the cough frequency is zero at a given visit, 0.5 will be added to ensure a non-zero number.

⁸ The baseline value will be defined as the average of valid weekly interval measurements prior to the first dose of study drug (e.g., average of Day -14 and Day -7). If one weekly interval measurement is missing or invalid, the non-missing, valid interval measurement will be used.

⁹ The baseline value will be defined as the Day 1 assessment.

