9.1.4 Early Termination of Treatment

If a subject prematurely discontinues study treatment, an Early Termination of Treatment (ETT) Visit should be scheduled as soon as possible after the subject decides to terminate study treatment. Subjects who prematurely discontinue treatment will also be required to complete the Safety Follow-up Visit.

If the ETT Visit occurs 3 weeks or later following the last dose of study drug, then the ETT Visit will replace the Safety Follow-up Visit, and a separate Safety Follow-up Visit will not be required.

If a subject withdraws from the study and also withdraws consent or assent, no further assessments will be performed. Vertex may retain and continue to use any data and samples collected before such withdrawal of consent or assent.

Wearable devices must be returned to the site during the ETT Visit.

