9.1.6 Completion of Study Participation

Completion of study participation for each individual subject is defined as 1 of the following:

- For subjects who complete the Treatment Period and enter an open-label extension safety study within 28 days of the Week 13 Visit: the Week 13 Visit
- For subjects who complete the Treatment Period and do not enter an open-label extension safety study within 28 days of the Week 13 Visit: the Safety Follow-up Visit
- For subjects who prematurely discontinue study drug treatment but do not withdraw consent (and assent, as applicable): the later of the ETT Visit or Safety Follow-up Visit (if required)
- For subjects who withdraw consent or assent: date of withdrawal of consent or assent, whichever is earlier (Section 9.9)

If subjects are lost to follow-up (Section 9.1.5), the date of completion of study participation will be defined as the date of the last contact.

The end of study is defined in Section 13.2.9.

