9.6 Administration

9.6.1 Dosing

Study drug tablets will be administered orally as ELX 200 mg qd/TEZ 100 mg qd/IVA 150 mg q12h (e.g., 2 ELX/TEZ/IVA fixed-dose combination [FDC] tablets in the morning and 1 IVA tablet in the evening). Additional information is provided in the Pharmacy Manual.

Study drug should be administered with a fat-containing meal or snack, such as a standard “CF” meal or snack or a standard meal according to the following guidelines:

1. It is recommended that the dose be taken within approximately 30 minutes of the start of the meal or snack.
2. All doses of study drug (morning and evening, as applicable) should be administered approximately every 12 hours (± 2 hours) on each dosing occasion (e.g., if the morning doses of study drug are administered at 08:00 hour on Day 1, all subsequent morning doses should be administered between 06:00 hour and 10:00 hour).
3. At the Day 1 Visit, all subjects will be observed for 2 hours after the morning dose of the study drug.
4. At the Day 1 Visit, the morning dose of study drug will be administered under the supervision of site medical staff after predose assessments have been completed. The meal or snack will be provided by the site on Day 1 for the morning dose of study drug.

5. Study drug will be dispensed at the Day 1 Visit. Subjects will be instructed to return all used and unused study drug to the site at the Week 13 Visit.
6. At the Week 13 Visit, the morning dose of study drug will NOT be administered. The last dose of study drug will be the evening dose administered the day before the Week 13 Visit.

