9 STATISTICAL ANALYSIS

9.1 General Considerations

Continuous variables will be summarized using the following descriptive summary statistics: the number of subjects (n), mean, SD, median, minimum value (min), and maximum value (max).

Categorical variables will be summarized using counts and percentages.

Baseline value, unless specified otherwise, will be defined as the most recent non-missing measurement (scheduled or unscheduled) collected before the first dose of study drug.

Absolute change from baseline will be calculated as post-baseline value – baseline value.

Relative change from baseline will be calculated and expressed in percentage as $100\% \times (\text{post-baseline value} - \text{baseline value}) / \text{baseline value}$.

Treatment-emergent (TE) Period will include the time from the first dose of study drug to 28 days after the last dose of study drug or to the completion of study participation, whichever occurs first.

Incomplete/missing data will not be imputed, unless specified otherwise.

Unscheduled visits: Unscheduled visit measurements will be included in analysis as follows:

- 1) In scheduled visit windows per specified visit windowing rules
- 2) In the derivation of baseline and last on-treatment measurements
- 3) In the derivation of maximum and minimum values during TE period, and maximum and minimum change from baseline values during TE period for safety analyses
- 4) In individual subject data listings as appropriate

Visit windowing rules: The analysis visit windows for protocol-defined visits are provided in Appendix A.

Outliers: No formal statistical analyses will be performed to detect or remedy the presence of statistical outliers, unless specified otherwise.

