9.2.5 Study Drug Exposure

Study drug exposure will be summarized based on the Safety Set.

Duration of study drug exposure (in weeks) will be calculated as: (last dose date of study drug – first dose date of study drug + 1)/7, regardless of study drug interruption.

Study drug exposure in weeks will be summarized descriptively by the number of subjects (n), mean, SD, median, min, and max. It will also be summarized by intervals using counts and percentages.

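### The SAP imputes a missing or partial last dose date from visits held after dosing has stopped, which overstates exposure, mainly for affected early stoppers

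*SAP*

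**What the plan says.** SAP Appendix A, Derived Variables item 3, covers a last dose date that is missing or only partly reported. It says that "the last dose date will be imputed based on, in descending order priority, the Early Treatment Termination (ETT) visit date", followed by "last visit date before the Safety Follow-up, or the last study drug administration date from EX SDTM domain, as appropriate". The dosing record is therefore third in a ranked list, with a closing qualifier that leaves some discretion. The one limit is this: "The imputation algorithm will ensure the imputed last dose date does not exceed the study participation end date". Nothing is said about using the month and year of a partial date.

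The protocol fixes where these visits fall relative to dosing. Section 9.1.4 schedules the ETT Visit after the subject decides to stop and sets no upper limit on the delay. It provides for a long one: "If the ETT Visit occurs 3 weeks or later following the last dose of study drug", the ETT Visit takes the place of Safety Follow-up. Section 9.6.1 says for completers: "At the Week 13 Visit, the morning dose of study drug will NOT be administered". Their last dose is on the evening before.

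Three SAP quantities depend on the last dose date:
- Exposure (9.2.5) is last dose date minus first dose date plus 1, divided by 7, with no deduction for interruptions.
- Compliance (9.2.6) divides interruption days by that duration in days. It does not count an interruption that lasts to the end of participation.
- The treatment-emergent period (9.1): "Treatment-emergent (TE) Period will include the time from the first dose of study drug to 28 days after the last dose", or to completion of participation if that comes first.

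**The concern.** An imputation rule for a dosing date would normally start from the dosing record and use visit dates to bound it. Here two visit dates outrank the record. In the ordinary cases (an ETT Visit, or a Week 13 Visit) the protocol itself makes them dates on which the subject is no longer taking drug. The cap at the end of participation does not help. Under Protocol 9.1.6, participation never ends before the ETT Visit for an early stopper who stays in the study, nor before the Week 13 Visit for a completer.

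Partial dates are treated differently elsewhere in the same SAP. Where only the day is missing, Appendix C takes the last day of the reported month for a medication stop date. Appendix D does the same for an adverse event end date, limited by the end of participation. Item 3 has no such bound, so a last dose known to fall in one month can be moved to a visit in a later month.

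At stake are the individual exposure, compliance and treatment-emergent values of affected subjects, chiefly those who stopped early.

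**Working it through.** The documents give no figure for this point, so there is none to reproduce. The SAP formulas were applied once with the true last dose day and once with the imputed visit day.

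**Inputs from the documents**
- Exposure days E = last − first + 1; weeks = E/7 (SAP 9.2.5).
- Compliance = 100 × (1 − I/E), where I is the number of counted interruption days; categories are split at 80% (SAP 9.2.6).
- Treatment-emergent end = the earlier of last dose + 28 days and the end of participation (SAP 9.1).
- Week 13 runs from Day 85 to Day 91 (Protocol Table 3-2, footnote on the 7-day window).
- Safety Follow-up is 28 ± 7 days after the last dose (Protocol 9.1.3).

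**Assumptions:** first dose on Day 1, last dose on Day 28, ETT Visit 1 to 28 days later, and 0, 3 or 7 interruption days that were followed by resumption.

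**Early stopper.** True exposure is 28/7 = 4.00 weeks. True compliance is 100 × (1 − 3/28) = 89.3% or 100 × (1 − 7/28) = 75.0%.

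| ETT lag (days) | Imputed weeks | Overstatement | Compliance, I = 3 | Compliance, I = 7 |
|---|---|---|---|---|
| 1 | 4.14 | +3.6% | 89.7% | 75.9% |
| 7 | 5.00 | +25% | 91.4% | 80.0% |
| 14 | 6.00 | +50% | 92.9% | 83.3% |
| 21 | 7.00 | +75% | 93.9% | 85.7% |
| 28 | 8.00 | +100% | 94.6% | 87.5% |

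With I = 0, compliance is 100% under either date. With I = 7, the subject moves from below 80% to the upper category once the lag reaches 7 days (1 − 7/35 = 80.0%).

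**Completer imputed from the Week 13 Visit.** Day 85: 85/7 = 12.14 weeks instead of 84/7 = 12.00. Day 91: 91/7 = 13.00 instead of 90/7 = 12.86. The difference is 1 day, about 1.1% to 1.2%. With 7 interruption days and a Day 85 visit, compliance is 91.8% instead of 91.7%.

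**Treatment-emergent end, last dose on Day 28 (28 + 28 = Day 56)**
- ETT on Day 49 (lag 21): it replaces Safety Follow-up, so participation ends on Day 49. True end: earlier of 56 and 49 = 49. Imputed end: earlier of 77 and 49 = 49. No change.
- ETT on Day 42 (lag 14), Safety Follow-up on Day 63: true end 56; imputed end: earlier of 70 and 63 = 63. Shift +7 days. With Safety Follow-up on Day 56 or before, the shift is 0.
- ETT on Day 63 (lag 35), ending participation: true end 56; imputed end: earlier of 91 and 63 = 63. Shift +7 days. In general, an ETT Visit that ends participation adds its lag beyond 28 days, and nothing up to 28 days.
- Completer: at most +1 day, and 0 for a subject who enters the extension study and so ends participation at the Week 13 Visit.

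**Effect on the mean.** Assume 5 of 100 subjects are affected, all early stoppers with a 21-day lag. Mean exposure then moves by 5 × 3.0/100 = 0.15 weeks, in a treatment period of about 13 weeks.

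**The case against.** The best defence is that the rule is rarely used and not rigid. It applies only to missing or partial dates. Drug counts at Day 1, Weeks 4, 8, 12 and 13 and the ETT Visit (Protocol Table 3-2), together with queries for missing data (Protocol 13.3), should keep such cases few. The closing qualifier lets the programmer depart from the order. If the last dose date is missing, the EX record may be incomplete too, and putting EX first could then give a date that is too early. A longer treatment-emergent period captures more events, which fits the SAP's choice in 9.4.1 to class adverse events of unclear onset as treatment-emergent.

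Much of this stands, and it rules out several stronger readings:
- A reader might infer that the error always lengthens exposure. It does not. A subject lost to follow-up may have neither an ETT nor a Week 13 Visit. SAP Appendix A, note 1, lets a visit be a telemedicine contact, so the last visit may fall while the subject is still dosing, and the imputed date may be too early.
- A reader might infer that compliance is generally inflated. It changes only when an interruption was followed by resumption.
- A reader might infer that adverse-event classification is seriously distorted. Only the end of the treatment-emergent period can move, by the limited amounts shown above.
- A reader might infer that a good EX date is always overridden. The qualifier does not require that, and the documents do not say that such a date will exist.

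What does not stand is that the qualifier cures the rule. It sits beside an explicit ranking and names no circumstance in which the ranking should be reversed.

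**Conclusion.** The point holds as a minor one. If the stated order is followed, an ETT Visit date overstates exposure by the full gap since the last dose, and a Week 13 Visit date overstates it by 1 day. The 4.0 versus 7.0 weeks and the 75.0% versus 85.7% compliance are illustrations. They rest on an assumed Day 28 last dose, a lag of 21 days (which the protocol provides for) and, for compliance, 7 resumed interruption days.

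The treatment-emergent end does not move when an ETT Visit ends participation within 28 days of the last dose. It moves by at most 7 days when Safety Follow-up falls in its window of 28 ± 7 days. The number of subjects affected is not given; it is probably small, and mean exposure would hardly change. The definitions of the cough and step-count endpoints (SAP 9.3.1.1 and 9.3.2.1) do not use the last dose date, so nothing here bears on the efficacy results. The defect lies in the derived values of individual affected subjects and in an inconsistency with the SAP's own partial-date rules.

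**What to change.** Amend SAP Appendix A, Derived Variables item 3, so that:
- a partial last dose date is imputed within its reported month and year, in line with Appendices C and D;
- a complete EX last administration date is used when it exists and agrees with the drug-count records;
- otherwise a visit date serves only as an upper bound, taking the day before the visit for Week 13;
- imputed last dose dates are flagged in the listing.

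The cost is a short SAP amendment and a small programming change, with no new data. The downside is that an incomplete EX record may give a date that is somewhat early. The agreement check and the flag make such cases visible.
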